2.6. Sample size calculation

For alpha of 0.05, power of 0.80, an estimated standard deviation of 0.6, and moderately expected effect size that is compatible with pooled analysis of previous studies comparing VR with other digital training environments,¹⁴ a sample size of 46 trainees is required to be able to show a statistically significant difference in results. Considering a potential dropout rate of 10%, a total sample size of 50 participants is needed.

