2.7. Statistical analysis

Data analysis will be performed using R version 3.6.1 (2019, The R Foundation for Statistical Computing). Categorical data will be presented as absolute frequency and associated percentage rate. Symmetrically distributed data will be presented as mean \pm standard deviation (SD). For independent samples, t-Test or Mann-Whitney U test, and for dependent samples, paired t-Test or paired Wilcoxon signed-rank test will be used to compare the performance differences according to the type and distribution

of variables. Reckoning with the study's crossover design, the comparison of continuous outcomes will be conducted using a linear mixed model, which assumes treatment (VR vs DI-based training) and period as fixed effects and resident as a random effect. To evaluate the risk of a carryover and learning effect between two sequences of tests, an interaction term *treatment x period* will be included in the mixed model to test for the presence of a carryover effect. Finally, the influence of resident gender and level (senior vs junior) on the outcomes will be explored by including in turn these variables into the model as fixed effects. An α level of $P < .05$ will be considered statistically significant and P values will be calculated 2-sided.

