2.8. Randomization

Using computer-generated randomization stratified by postgraduate (PG) level (Junior (PG 1-2) vs Senior (PG ≥ 3)) and institution, residents will be randomized in a 1:1 allocation to one of two assessment sequences to devise a surgical plan for 10 clinical scenarios. In group A, the first five cases will be evaluated via a DI, and the second five cases will be evaluated in the VR environment; while in group B, the sequence of cases will be reversed. We consider one-hour washout time between the first and the second sequence of cases.

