3.1. Primary outcome

- The difference in accuracy of the residents' decision-making when reviewing patient data along with 3D liver models visualized via DI or VR, measured by comparing their performance to experts' opinion.

3.2. Secondary outcomes:

- Percentage of residents achieving proficiency in clinical decision-making after completing the training curriculum
- The difference in the timing to devise treatment plans using DI or VR
- Percentage of correct anatomical landmark and liver segments identification using DI or VR
- Knowledge retention assessed by comparing MCQs score before and after e-learning training

4. Cross-over randomized trial

After signing informed consent, all participants will complete a pre-training questionnaire to determine their demographic information and their experience in liver surgery. Then, they will answer a set of 15 MCQs to assess their baseline cognitive knowledge. Subsequently, they will receive the 3 e-learning models to study. After completion of e-

learnings, 15-MCQ will be provided. When the average MCQ score (i.e. at least 80%) of the experts (benchmark) has been achieved, they can progress to the next training step. If they will not accomplish the required score, they are referred to the e-learning platform and once they feel ready, a second different set of MCQ should be completed until they reach the benchmark score. They will have one month time to study the modules and associated tests on their own pace.

For the next step, residents will be invited to an individualized training session for 3D anatomy training and clinical decision-making. Participants will be trained individually by an investigator to be able to interact with SYNAPSE VINCENT and LiVeR Trainer. After completing the training session, the two groups will be compared for accuracy of their surgical planning when they used DI or VR to review 3D models of liver during surgical planning. Group A will receive the first 5 cases along with 3D models via DI and the second 5 cases in the VR environment, while group B will receive a reverse sequence of cases.

5. Ethics

The institutional review board at Ghent University Hospital reviewed and approved the protocol (IRB approval No. B6702020000275). Participation of trainees will be voluntary and informed consent will be obtained from all of them.

6. References

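### The treatment x period term in Section 2.7 cannot isolate carryover, does not respond to learning common to both groups, and is too imprecise to rule carryover out; the plan should say that the VR-DI estimate comes from the model without it

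*Combined protocol and SAP*

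**What the plan says.** Section 2.7 states that "the comparison of continuous outcomes will be conducted using a linear mixed model", with treatment (VR or DI) and period as fixed effects and resident as a random effect. It then gives an aim, "To evaluate the risk of a carryover and learning effect between two sequences of tests", and a means: a treatment x period term that "will be included in the mixed model to test for the presence of a carryover effect". It does not say how a significant or non-significant term will be interpreted. Nor does it say whether the reported VR-DI estimate comes from the model with the term or without it. The software is R.

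Section 2.8 randomises residents 1:1 to two sequences. Group A uses DI for the first five cases and VR for the second five; "in group B, the sequence of cases will be reversed". On the gap between the two sets: "We consider one-hour washout time between the first and the second sequence of cases". Section 2.6 gives 46 trainees before dropout, so 23 per sequence.

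**The concern.** In a two-sequence, two-period crossover there are only four cell means. Once the intercept, treatment and period are fitted, one contrast is left. The plan gives that contrast a specific meaning (carryover) and a second task (learning), and the design supports neither.

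The stakes are in interpretation. A significant term would be reported as carryover although other mechanisms give the same result. A non-significant term could be taken as evidence that a one-hour washout was enough, although the test would miss most carryover differences of a size that matters to the VR-DI estimate. Separately, if the term stays in the reported model and the treatment coefficient is read under R's default coding, the quantity estimated changes and precision is lost.

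**Working it through.** **Inputs.** From the plan: 46 residents (Section 2.6), two sequences at 1:1 (Section 2.8), two-sided 5% tests (Section 2.7). Assumed: group B is VR then DI; complete, normal data; per-period SD of 1; within-resident correlation rho of 0, 0.3 or 0.5. Results are in SD units because Section 2.6 does not say to which outcome or scale its SD of 0.6 refers.

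**The plan's own figure.** Section 2.6 gives no numerical effect. With an assumed raw difference of 0.5, the two-sample formula gives 2 x (1.960 + 0.842)^2 x 0.6^2 / 0.5^2 = 22.6, so 23 per group and 46 in all. The figure is attainable, cannot be verified from the plan's inputs, and is not disputed here.

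**Step 1: what the term estimates.** Let t be the VR effect, p a period shift common to both groups, cD and cV the carryover from DI and from VR, and g a group B minus group A difference. Measured from group A in period 1, the cell means are:

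- A1 = 0 (DI)
- A2 = t + p + cD (VR)
- B1 = t + g (VR)
- B2 = p + cV + g (DI)

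The interaction is (A2 - B2) - (B1 - A1) = A1 + A2 - B1 - B2 = cD - cV - 2g. If the VR effect is t1 in period 1 and t2 in period 2, t2 - t1 is added. So:

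- It is the contrast of resident totals between sequences. In -1/+1 coding its column over A1, A2, B1, B2 is (1, 1, -1, -1). Adding a sequence term gives five columns of rank 4, and in a simulated dataset the interaction and sequence p-values were identical (0.917).
- The common shift p cancels. In 20,000 simulated trials (SD 0.6, rho 0.5) a common learning gain of 0.5 made the term significant in 5.1%, its null rate, and the period effect in 100%.
- Equal carryover from both media (cD = cV) also cancels.

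**Step 2: the other contrasts.**

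- VR-DI without the interaction: [(A2 - A1) + (B1 - B2)] / 2 = t + (cD - cV)/2. It is free of p and g, and biased by half the carryover difference, in either direction.
- Period effect: [(A2 - A1) + (B2 - B1)] / 2 = p + (cD + cV)/2. It contains average carryover as well as common learning and fatigue.
- Period-1 contrast: B1 - A1 = t + g. It is free of carryover.

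**Step 3: precision.** Variances with 23 per sequence: interaction 4(1 + rho)/23; VR-DI without the interaction (1 - rho)/23; period-1 contrast 2/23. The t quantile on 44 df is 2.015; power is from the noncentral t.

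| | rho 0 | rho 0.3 | rho 0.5 |
|---|---|---|---|
| SE of interaction | 0.417 | 0.475 | 0.511 |
| 95% half-width | 0.84 | 0.96 | 1.03 |
| Half of that: bias compatible with an exactly null term | 0.42 | 0.48 | 0.51 |
| Power for a 0.5 SD carryover difference | 22% | 18% | 16% |
| Carryover difference needed for 80% power | 1.19 | 1.36 | 1.46 |
| Variance ratio, period-1 contrast to VR-DI without interaction | 2.0 | 2.9 | 4.0 |

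The bias row attributes the whole term to carryover.

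**Step 4: with or without the term.** In one simulated dataset (rho 0.5), the model without the interaction gave a treatment effect of 0.379 (SE 0.143). With the interaction under reference coding it gave 0.512 (SE 0.269), exactly the raw period-1 difference. With the interaction under centred coding it gave 0.379 (SE 0.143) again. The loss therefore arises only from keeping the term and reading the reference-coded coefficient. In that event, power for an assumed 0.5 SD effect falls from 65%, 80% and 91% to 38%.

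**The case against.** Several points on the other side stand.

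- The aliasing belongs to every two-by-two crossover, and calling this term a carryover test is conventional. The fault is the property claimed for the term, not the design.
- Section 2.7 does name a model. Reading it as a main-effects comparison with a diagnostic term added is fair.
- Residents are randomised with stratification, so chance differences between the groups are already in the term's variance. A group difference is a rival explanation only beyond chance. The treatment-by-period effect remains a rival in any case.
- Common learning is already adjusted for by the period effect. If learning here means modality-specific transfer, the term does respond to it, but that is carryover and should be named so.
- Residents are trained in both environments until they can work independently (Section 2.3), and each period uses different cases. Both plausibly limit differential carryover; neither rules it out.
- The correlations and carryover sizes are assumed, and the plan does not say that a non-significant term will be taken as clearing carryover.

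These points limit the finding but do not answer it. The text still assigns the term a task that it cannot perform, and leaves open whether it stays in the reported model.

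**Conclusion.** The concern holds for outcomes analysed with the mixed model. That the term is not specific to carryover and does not respond to common learning is algebra, given group B as VR then DI. Its imprecision depends on the assumed correlation, but the conclusion is the same from 0 to 0.5: even an exactly null term leaves room for a bias of 0.42 to 0.51 SD in either direction, and a non-significant term away from zero leaves more on one side.

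A reader might infer more than the documents support:

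- *That the plan tests for carryover and then chooses its analysis.* Section 2.7 contains no such rule.
- *That the VR-DI comparison is invalid or underpowered.* The model without the interaction is a sound within-resident comparison. The two- to fourfold variance applies only under the reading in Step 4.
- *That carryover is present.* Nothing in the documents shows this.
- *That the primary outcome is affected.* The plan does not say whether accuracy over five cases is treated as continuous, so this is not established.

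The wording of group B's modality and case order in Sections 2.8 and 4 needs its own clarification and is not part of this point.

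**What to change.** In Section 2.7, for outcomes analysed with the mixed model, state:

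- The VR-DI estimate comes from the model with treatment and period as fixed effects and resident as a random effect, without the interaction, whatever the interaction shows.
- The period effect is reported as the overall period difference: common learning, fatigue, average carryover and, if case sets are fixed by period, case difficulty (not separable).
- The treatment x period term is reported from a separate sensitivity model with its estimate and 95% confidence interval, labelled sequence / carryover / treatment-by-period (not separable). A non-significant result is not taken as absence of carryover.

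The period-1 contrast may be added as a sensitivity result.

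The cost is a few sentences and no new data. The downside should be stated: if differential carryover is real, the reported estimate is biased by half its size. The period-1 contrast avoids that bias but has 2 to 4 times the variance at rho 0 to 0.5. The two have equal mean squared error when the carryover difference is 2 x sqrt((1 + rho)/23), that is 0.42, 0.48 or 0.51 SD. At that point the interaction is one standard error from zero and significant in only 16.5% of trials, so its p-value is a poor basis for choosing between them.

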2.8. Randomization

Using computer-generated randomization stratified by postgraduate (PG) level (Junior (PG 1-2) vs Senior (PG ≥ 3)) and institution, residents will be randomized in a 1:1 allocation to one of two assessment sequences to devise a surgical plan for 10 clinical scenarios. In group A, the first five cases will be evaluated via a DI, and the second five cases will be evaluated in the VR environment; while in group B, the sequence of cases will be reversed. We consider one-hour washout time between the first and the second sequence of cases.

2.9. Criteria for selecting the radiologic imaging

CT scans used in this study will be taken from a library of CT scans of patients with liver tumors who underwent liver surgery at Ghent university hospital. Ten patient

cases will be selected based on quality images that provide adequate visualization for surgical planning and reflect the intraoperative findings, as the final surgery performed was in line with the preoperative plan. Each preoperative image will be independently reviewed by two hepatobiliary surgeons to provide expert opinion on the optimal surgical plan, and cases with differing opinions will be excluded.

A total of 10 cases will be selected and patient data will be anonymized.

CT images will be imported into the FUJIFILM synapse 3D software, to produce 3D surface renderings of the liver surface, hepatic veins, portal veins, hepatic arteries and tumor. The same 3D model will be uploaded to the VR environment.

Various liver cases (benign and malignant) will be considered, and the final 10 cases will include the following surgical plan:

1. Left lateral resection
2. Left hepatectomy
3. Right hepatectomy
4. Extended right hepatectomy
5. Multiple wedge resection (cherry-picking metastasectomy)
6. Right posterior sectionectomy
7. Unresectable tumor due to main portal vein invasion
8. Central hepatectomy
9. Anatomical resection of segment 7
10. Unresectable tumor due to low volume of future liver remnant

3. Endpoints

3.1. Primary outcome

- The difference in accuracy of the residents' decision-making when reviewing patient data along with 3D liver models visualized via DI or VR, measured by comparing their performance to experts' opinion.

3.2. Secondary outcomes:

- Percentage of residents achieving proficiency in clinical decision-making after completing the training curriculum
- The difference in the timing to devise treatment plans using DI or VR
- Percentage of correct anatomical landmark and liver segments identification using DI or VR
- Knowledge retention assessed by comparing MCQs score before and after e-learning training

4. Cross-over randomized trial

After signing informed consent, all participants will complete a pre-training questionnaire to determine their demographic information and their experience in liver surgery. Then, they will answer a set of 15 MCQs to assess their baseline cognitive knowledge. Subsequently, they will receive the 3 e-learning models to study. After completion of e-

learnings, 15-MCQ will be provided. When the average MCQ score (i.e. at least 80%) of the experts (benchmark) has been achieved, they can progress to the next training step. If they will not accomplish the required score, they are referred to the e-learning platform and once they feel ready, a second different set of MCQ should be completed until they reach the benchmark score. They will have one month time to study the modules and associated tests on their own pace.

For the next step, residents will be invited to an individualized training session for 3D anatomy training and clinical decision-making. Participants will be trained individually by an investigator to be able to interact with SYNAPSE VINCENT and LiVeR Trainer. After completing the training session, the two groups will be compared for accuracy of their surgical planning when they used DI or VR to review 3D models of liver during surgical planning. Group A will receive the first 5 cases along with 3D models via DI and the second 5 cases in the VR environment, while group B will receive a reverse sequence of cases.

5. Ethics

The institutional review board at Ghent University Hospital reviewed and approved the protocol (IRB approval No. B6702020000275). Participation of trainees will be voluntary and informed consent will be obtained from all of them.

6. References

